Although CRF is well documented, it is difficult to characterize because it has a poorly delineated etiology. Circadian rhythm disruption (CRD) has been hypothesized to play an important role in the etiology of CRF by affecting multiple domains of psychosocial and physiological functioning. Circadian rhythms are generated and regulated by an internal biological clock located in the suprachiasmatic nucleus of the hypothalamus; they are biological cycles (e.g., changes in hormone secretion, body temperature, and sleep-wake activity cycles) that are slightly longer than 24 hours and are entrained to the 24-hour day by environmental time cues.

Bright light is one of the strongest synchronizers of circadian rhythms, which are maintained through entrainment by light exposure to the retina. Light therapy incorporating systematic exposure to bluish-

	Protocol Name:	Systematic Programmed Illumination of Hospital Rooms to Prevent/Reduce Cancer-Related Fatigue during Autologous Stem Cell Transplantation for Multiple Myeloma
	Principal Investigator:	[name]; [contact]
	Primary Contact Name/Contact Info:	[name], [contact], [contact]
	Date Revised:	8/15/2019
	Study Number:	IF# 2517160 HS# 15-00777 GCO#: 15-2009

white light is hypothesized to entrain circadian rhythms, which play a crucial role in the cellular and physiological functions of the brain and body. Indeed, disruption of these rhythms has been shown to affect sleep quantity and quality, depression, and fatigue among cancer patients. The proposed research will investigate the delivery of sPI via a novel delivery system to treat CRF, experienced by up to 80% of all cancer patients. Although CRF has been found to be related to CRD and it is known that bright light improves rhythms, the effect of sPI on CRF has not been investigated. Further, CRF has been found to be related to sleep disturbances, as well as to depression, yet the effect of sPI on these effects has not been explored.

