Inflammatory response have been proposed to underlie CRF. There is an association between CRF among cancer patients and activation of pro-inflammatory signaling. For example, breast cancer survivors with persistent fatigue have elevated levels of markers associated with pro-inflammatory cytokine activity including Interleukin-1 receptor antagonist (IL-1ra), Interleukin-6 (IL-6), soluble tumor necrosis factor receptor type II (sTNF-RII), soluble intercellular adhesion molecule-1 (sICAM-1), and C-reactive protein (CRP). It has also been shown that chemotherapy leads to significant elevations in inflammation which is associated with increases in fatigue.

In the proposed preliminary feasibility research, sPI will deliver appropriately timed ambient, low-level, bluish-white light to patients during their hospital stay with floor lamps designed to deliver high circadian stimulation in the morning. We have selected cancer patients who are hospitalized for HSCT to treat MM because this population: (1) is relatively homogenous with a high prevalence of CRF, (2) can be studied prospectively across the course of HSCT, (3) permits careful monitoring of circadian rhythm entrainment through analysis of melatonin from urine obtained before, during and after HSCT, (4) regularly has blood drawn for clinical purposes and (5) allows assessment and control of confounding variables.

Preliminary research:

The proposed exploratory study builds on [name]’s, [name]’s, and [name]’s complementary areas of research. [name], [name] and colleagues’ ongoing investigation of BWL to treat CRF in cancer (including HSCT) survivors has formed the conceptual template for the proposed study and points to the potential importance of sPI in the prevention and treatment of CRF. In previous studies, they were able to retain 71% of participants, a retention rate that we also expect for the proposed protocol.

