Acuity Lighting Brands will be providing the lighting fixtures in patient rooms at no cost. The fixtures will control all emitted wavelengths and provide both treatment and comparison conditions from the same fixture, as controlled by the investigators.

Methods: MM patients who will receive an autologous HSCT as part of their treatment plan will be recruited from MSH, and will be randomly assigned to either the BWL or the DWL conditions. Participants in both treatment arms will complete baseline 1 assessment at the time they are recruited. If Baseline 1 is completed more than two months before transplant participants will complete baseline 2 approximately one month before their transplant. After the baseline(s) assessment participants will be assessed: (A) during the inpatient hospital stay at day of transplant, day + 2, day + 7; (B) engraftment day 3 (most likely during week 2-3); (C) one month after hospital discharge; and (D) three months after hospital discharge. Outcome measures include standardized questionnaire measures of CRF, depression, sleep quality, and quality of life, as well as analysis of urinary melatonin and blood inflammatory marker levels at both outpatient and inpatient timepoints to monitor the biological processes believed to be influenced by sPI. This assessment schedule will allow us to evaluate the immediate and post-treatment benefits of the sPI treatment.

The proposed statistical analyses examine a number of related questions. The first consists of a comparison of the impact of the sPI exposure intervention to a comparison condition on CRF, depression, sleep quality, circadian rhythmicity, and quality of life using both the self-report and objective outcome measures (i.e. actigraphy data) in MM patients undergoing autologous HSCT. The second will examine the possible mediating role of depression, sleep quality, circadian activity rhythms, and fatigue on the effects of sPI. Lastly, the third will assess the feasibility and acceptability of an sPI intervention, actigraphy, urine melatonin analysis, and light exposure monitoring during HSCT. We will also look at possible co-moderators that may influence for whom the treatment works as defined by the list of additional measures we have included. In addition, we will explore whether the light treatment improves fatigue and depression through biological mediators analyzed in blood, i.e. inflammatory markers.

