of Life), hierarchical random effects linear mixed models will be employed for Aims 1 and 2 using MIXED with repeated measures. Besides time (linear and possibly quadratic trends to allow for possible nonlinear trends), any covariates identified in the preliminary analyses and intervention group will be assessed in a fixed effects model. Each model will also include a random intercept. Post-hoc comparisons will be Tukey-adjusted. Since there are multiple secondary outcomes, the p-values will be Sidak adjusted for correlated multiple comparisons. Any variations in length of hospital stay (i.e., length of intervention) will be used as a covariate in all analyses. This is highly unexpected since 90% of ASCT patients are hospitalized for 14 days. In the Analysis of Aim 2, we will establish that the treatment is a significant predictor of the primary outcome (CRF) as well as the hypothesized mediators. Next, we will first examine the role of each of the mediators of the effects of sPI on CRF by introducing each individually into the equation which contains the time variable, the treatment main effect, and the time by treatment interaction. Each mediator which is a significant predictor of CRF in this equation will then be combined with any other significant mediating predictor of CRF into a single equation. We predict the introduction of each significant mediator will result in the decrease in the significance of the time by treatment interaction effect on CRF. However, the more important test of the mediating role by any variable will depend on the statistical significance of the indirect path from treatment to mediator and from mediator to the outcome. Following procedures suggested by Shrout and Bolger (2002), 1000 bootstrap samples will be employed to determine the significance of each indirect path.⁵⁰ **Power:** It is difficult to discuss power for **Aim 1** and **Aim 2** since there is no directly relevant past research. As a consequence, one of the goals of this project is to obtain estimates of the effect sizes that will eventuate from our proposed analyses. Although unknown at the moment, these effect sizes can guide decisions regarding sample sizes for a larger scale grant. In the interim, there are three lines of research that may provide some guidance. The first involves the work of [name], who investigated the effects of light treatment on fatigue experienced by women undergoing chemotherapy for breast cancer.⁹ Using her results, we calculated power for a repeated measures design with an autoregressive lag 1 structure and autocorrelations ranging from 0.40 to 0.60. With alpha equal to 0.05 and a sample size of 30 patients per group, power ranged between 0.96 and 0.98. We followed a similar approach using [name]'s results but focusing only on MM survivors of ASCT.¹⁰ In this case, power was 0.99 for autocorrelations ranging between 0.40 and 0.60. However, the latter results must be treated cautiously because these calculations were based on a very small sample (N = 17 survivors). Using the same small sample, our repeated measures analysis of depression indicated that the time by treatment condition interaction was marginally significant (p = 0.0568). The F-ratio for this interaction yielded an eta coefficient of 0.48 which would be considered moderately strong following Cohen's criteria.⁴⁹ We hypothesize that the interaction effect would have been significant had the sample size been larger as is being proposed in this study (N = 60). Because of the very small survivors sample and the variability of our indicator of circadian activity rhythms (the f-statistic), the Mixed program did not converge and it was not possible to obtain a power estimate for this outcome. The third line of research that is germane to power in the proposed pilot study was conducted by Sim and Lewis who applied the UCL approach and found that a pilot sample of n => 55 would minimize the overall sample size for small to medium standardized effect sizes (0.2-0.6).

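### In Aim 2 the mediator-to-fatigue path absorbs the shared transplant course and stable patient differences, so when light changes both fatigue and another variable, that variable can be reported as a mediator without driving fatigue

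*Combined protocol and SAP*

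**What the plan says.** The Data Analysis text in section 5(g) uses one family of mixed models for Aims 1 and 2. The time terms are set out as "Besides time (linear and possibly quadratic trends to allow for possible nonlinear trends", and "Each model will also include a random intercept".

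For Aim 2 the steps run in order:

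- First, "we will establish that the treatment is a significant predictor of the primary outcome (CRF) as well as the hypothesized mediators".
- Each mediator is then tested by "introducing each individually into the equation which contains the time variable, the treatment main effect, and the time by treatment interaction". Those that predict fatigue significantly go together into one equation.
- The test the plan ranks highest is the indirect path, treatment to mediator to fatigue: "1000 bootstrap samples will be employed to determine the significance of each indirect path".

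The text states no categorical visit effect, no separation of within-patient from between-patient mediator differences, no baseline mediator value, no lag and no resampling unit.

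Section 5(e) schedules assessments at baseline, then "during the inpatient hospital stay at day of transplant, day + 2, day + 7", then at engraftment and at one and three months after discharge. The Background (section 2) says that "chemotherapy leads to significant elevations in inflammation which is associated with increases in fatigue" and that "CRF has been found to be related to sleep disturbances, as well as to depression".

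**The concern.** Randomisation protects the comparison of arms on the mediator. It does not protect the link from mediator to fatigue, which is observational. Two things can make that coefficient non-zero when neither variable affects the other.

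- **Shared course.** The visits span an acute insult and a recovery. If fatigue and the mediator both dip around transplant, and a line or parabola does not follow the dip, the leftover common pattern is attributed to the mediator.
- **Stable differences.** A single mediator term in a random-intercept model blends within-patient and between-patient association. If patients who sleep badly in general are also more fatigued in general, that counts as evidence of a path.

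The Background gives reason to expect both. Bootstrapping the product of the two paths measures sampling error and leaves this bias in place.

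The exposed case is the one Hypothesis 1a predicts: light improves fatigue and also improves sleep, mood and activity rhythm. The analysis then cannot tell a variable that carries the fatigue effect from one that merely responds alongside it. Separating those two is the purpose of Aim 2.

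**Working it through.** **The plan's own figure.** The documents give no power or error rate for the mediation test. The nearest figure is power of 0.96 to 0.98 for fatigue with 30 per group and alpha 0.05. It cannot be reproduced, because effect size, SD and number of repeated measures are not given. As one two-sided two-sample comparison it implies d = (1.960 + z) × √(2/30):

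- power 0.96: (1.960 + 1.751) × 0.258 = 0.96
- power 0.98: (1.960 + 2.054) × 0.258 = 1.04

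On the plan's own expectation, then, the requirement that treatment predict fatigue would almost always be met and would screen out little.

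**How much of a dip the trend leaves.** Assume visits at about days −30, 0, 2, 7, 14, 44 and 105, and a common course of 0, −0.3, −0.6, −1, −0.8, −0.3, −0.1 times the depth D.

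- Sum of squares about the mean at D = 1: 2.19 − 3.1²/7 = 0.817.
- A line in days removes 19.79²/11,229 = 0.035 and leaves 0.782 (96%).
- A parabola in days leaves 0.418 (51%); a parabola in visit number leaves 0.102 (13%).

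With residual variance 0.5 on 6 within-patient degrees of freedom (3.0 in all), and ignoring any light effect, the spurious within-patient slope is about D²R/(D²R + 3), where R is the sum of squares left. At D = 1 this is 0.782/3.782 = 0.21, 0.418/3.418 = 0.12 and 0.102/3.102 = 0.03. At D = 0.5 it is 0.06, 0.03 and 0.01. Depth and time coding therefore drive the answer.

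**Simulated false-mediation rates.** The true mediator effect is zero throughout. The 0.8 SD runs used 400 trials per scenario (Monte Carlo standard error at most √(0.25/400) = 2.5 points), 30 per arm unless stated, seven visits unless stated, intraclass correlation 0.5, a dip deepest at days 7 to 14, and 1000 patient-level bootstrap samples. None of the dip depth, intraclass correlation, light effects or time coding comes from the documents.

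| Scenario | Line, days | Parabola, days | Parabola, visit number |
|---|---|---|---|
| 1 SD dip, light 0.8 SD on both: indirect path significant | 85% | 64% | 44% |
| Same, every stated condition met | 78% | 57% | 36% |
| 1 SD dip, light 0.5 SD on both: every condition met | 63% | 37% | 10% |
| 1.5 SD dip, light 0.8 SD on both: every condition met | 86% | 85% | 72% |
| 1 SD dip, 0.8 SD, 21 per arm (71% retained): every condition met | 57% | 37% | 24% |
| No dip, patient-level correlation 0.5, 0.8 SD: every condition met | 59% | 32% | 35% |
| 1 SD dip, 0.8 SD, four visits as for blood: every condition met | 20% | 13.5% | 9% |

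With a 0.5 SD dip and 0.5 SD light effects, about 5% to 15% meet every condition.

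**Where the stated conditions do protect.**

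- *Light does not move the mediator (1 SD dip).* The mediator coefficient is falsely significant in 92%, 69% and 24% of trials, but the indirect path in only 4.5%, 2.8% and 0.7%.
- *Light moves the mediator by 0.5 SD but not fatigue.* The indirect path alone is significant in 70% (line) and 34% (parabola in days) at a 1 SD dip. Requiring treatment to predict fatigue and mediator cuts this to 2.8% and 1.5%. At a 1.5 SD dip, 86% and 81% become 4.8% and 4.7%.
- *Two visits, as for urinary melatonin.* A line already fits two points exactly, and the indirect path is significant in 2.2%.

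**After the change (indirect path alone, light 0.8 SD on both).** Visit as a category with only a linear time-by-treatment term gives 8.3%; full visit-by-treatment terms give 4.5%; adding the split of the mediator gives 3.7%. With no dip but a patient-level correlation of 0.5, visit-by-treatment with an unsplit mediator still gives 26%, and the split brings it to 3.5%. Both parts are needed.

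**The case against.** The strongest reply is that the plan does not rest on the mediator coefficient. It first requires treatment to predict fatigue and the mediator, and then tests the product of the two paths. This stands, and it limits the point. A reader might infer that any variable following the transplant dip would be declared a mediator; the stated conditions prevent that unless light moves both variables. They do not help when it does.

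Three further replies also stand in part.

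- **Scope.** A reader might extend the point equally to all of Hypotheses 2a to 2d. Section 5(f) has urine at two points, so the trend problem does not reach melatonin, and blood at four, where it is weaker. Section 5(e) also has a line scale replacing the FACIT-Fatigue for daily inpatient ratings, so a seven-visit series on one fatigue scale is not assured.
- **Inputs.** The size is assumed, not documented. A parabola in visit number, which the plan permits, does much better than a line in days, and a shallow dip leaves little excess.
- **Remedy.** A reader might take visit categories plus centring as a full cure. They are not one. If the depth of the dip varies between patients and is shared by both measures, the revised analysis still gives a false indirect path in about 16% to 20% of trials when the SD of depth is 0.5, and 59% when it is 1.0.

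Aim 2 is also worded as exploratory within a feasibility study, which limits the consequence. It does not make an avoidable bias worth keeping.

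**Conclusion.** The concern holds in a limited form. As specified, the mediator-to-fatigue path is open to bias from the common transplant course and from stable between-patient correlation. When light changes both fatigue and another variable, that variable can meet every stated condition and be reported as a mediator though it does not drive fatigue. When light leaves either one alone, the false rate stays near or below nominal.

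With a 1 SD shared dip the rate is roughly 10% to 78%, depending on the light effects and time coding; with a 0.5 SD dip and 0.5 SD light effects it is about 5% to 15%. These figures show what could happen under assumed inputs and are not forecasts for this trial. The point bears mainly on sleep, depression and activity rhythm (Hypotheses 2a to 2c) and less on blood markers (2d). For melatonin the trend part does not apply. The documents do not support concluding that a later trial would be built on the wrong mechanism: section 5(g) says only that the effect sizes may guide its sample size. The change should be made, but the trial does not depend on it.

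**What to change.** In the Aim 2 equations:

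1. Replace the linear or quadratic trend with visit as a categorical factor, with visit-by-treatment terms.
2. Enter each mediator as the patient's mean and the visit's deviation from that mean, and take the mediator-to-fatigue path from the deviation.
3. Define the treatment-to-mediator path as the baseline-adjusted difference between arms over the in-hospital visits.
4. Bootstrap the product of the two paths by resampling whole patients, and say so.
5. State that this does not remove reverse causation or confounding that varies over time, such as a patient-specific severity of the transplant course shared by both measures, and that Aim 2 results remain exploratory.

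The cost is wording and slightly more programming, with no new data, visits or patients. There is a small loss of power for the mediator-to-fatigue path: in simulation from 0.87 to 0.83 when the true coefficient is 0.15, and no material loss at 0.2 or above, because between-patient differences no longer count as evidence.

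### Aim 2's deciding mediation test uses only 1000 bootstrap samples, so a near-threshold verdict can turn on the random seed; use 10,000 and confirm that whole patients are resampled (minor)

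*Combined protocol and SAP*

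**What the plan says.** The analysis of Aim 2 is in the Data Analysis text of section 5(g) of the combined protocol and SAP. It first says "we will establish that the treatment is a significant predictor of the primary outcome (CRF) as well as the hypothesized mediators". Each mediator is then added to "the equation which contains the time variable, the treatment main effect, and the time by treatment interaction", and those that predict fatigue are combined in one equation. The plan then states that "the more important test of the mediating role by any variable will depend on the statistical significance of the indirect path", and that "1000 bootstrap samples will be employed to determine the significance of each indirect path". That sentence also cites a published mediation procedure.

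On the model being bootstrapped, the same section says that "hierarchical random effects linear mixed models will be employed for Aims 1 and 2 using MIXED with repeated measures" and "Each model will also include a random intercept".

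The text does not state the interval type, the seed, the unit that is resampled, or whether the whole model is refitted in each sample. Section 1 words Aim 2 as exploratory.

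**The concern.** A bootstrap verdict contains two kinds of chance. One is sampling of patients, which the method is meant to measure. The other is the finite number of draws, which is noise added by the computer and can be made as small as one likes. With 1000 draws the second kind is still large enough to move a borderline indirect path across the 5% line. Two analysts with the same data and the same code, but different seeds, could then report different mediators.

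A second question follows from the design. Patients are measured repeatedly (section 5(e) lists assessments "during the inpatient hospital stay at day of transplant, day + 2, day + 7", and more before and after) and treatment is assigned by patient. A bootstrap of such data should draw whole patients. The plan leaves the unit unstated, so this needs confirming.

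**Working it through.** **The plan's own figures.** The plan gives no error rate for the mediation test, so there is none to reproduce. Its power of 0.96 to 0.98 concerns the repeated-measures comparison. It cannot be recomputed, because the effect size and SD are not given, and it does not bear on this point.

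**Inputs.** From section 5(g): B = 1000 draws; alpha 0.05 and 30 patients per group; lag-1 autocorrelation 0.40 to 0.60. From section 5(e): six assessments after baseline plus one or two baselines, so 7 to 8 at most. From section 5(f): four blood draws and two urine collections. Assumed: a two-sided test and a 95% percentile interval.

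**Step 1: dependence on the seed.** A percentile interval excludes zero when at most 2.5% of draws fall on the far side of zero, that is 25 of 1000 or 250 of 10,000. Let p be the two-sided value that unlimited draws would give on the same data. The count on the far side is then binomial with B trials and probability p/2.

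| Exact p | Tail p/2 | Wrong verdict, B = 1000 | Wrong verdict, B = 10,000 |
|---|---|---|---|
| 0.03 | 0.015 | P(X > 25) = 0.6% | below 0.01% |
| 0.04 | 0.020 | P(X > 25) = 11.0% | P(X > 250) = 0.025% |
| 0.06 | 0.030 | P(X ≤ 25) = 20.4% | P(X ≤ 250) = 0.15% |
| 0.07 | 0.035 | P(X ≤ 25) = 4.6% | below 0.01% |

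Equivalently, at p = 0.05 the Monte Carlo standard error is 2 × √(0.025 × 0.975 / B). This is 0.0099 for B = 1000 and 0.0031 for B = 10,000.

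The result depends on convention. If the p-value were instead a single two-sided proportion judged against 50 of 1000, the errors at 0.04 and 0.06 would be about 5% and 10%. This is one reason to name the interval type.

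**Step 2: what the resampling unit would do, if it were the single record.** For a between-patient effect judged with record-level variance, the false-positive rate is about 2Φ(−1.96/√DE). Here DE = 1 + (m − 1)ρ for equal correlation, and DE = 1 + 2Σ(1 − k/m)ρ^k, summed over k = 1 to m − 1, for lag-1 autoregression.

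- m = 7, ρ = 0.4 to 0.6, equal correlation: DE = 3.4 to 4.6, rate 29 to 36%.
- m = 7, autoregressive: DE = 2.02 to 2.96, rate 17 to 25%.
- m = 2 (melatonin): DE = 1.4 to 1.6, rate 10 to 12%.

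A simulation of the full indirect effect a × b, with no treatment effect on the mediator (a = 0), checks this. It used 60 patients, complete data, a random-intercept fit with fixed variance ratio, 600 trials and 400 draws each.

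| Setting, ρ = 0.4 to 0.6 | Record-level draws |
|---|---|
| Treatment main effect, b = 0.5, 6 or 8 visits, autoregressive | 23 to 38% |
| Same, equal correlation | 40 to 59% |
| Treatment main effect, b = 0.5, 2 visits | 20 to 27% |
| Time-by-treatment effect, b = 0.5, 4 to 8 visits, autoregressive | 8 to 21% |
| Same, equal correlation | about 5% |
| Treatment main effect, b = 0, 6 visits | 2 to 5% |
| Treatment main effect, b = 0.5, with a valid treatment-to-mediator test passed first | 4 to 7% |

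With whole-patient draws the rate was 4.7 to 7.5% in every setting with b = 0.5.

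**The case against.** The strongest reply is that the seed effect is narrow and the aim modest. It touches only results close to 0.05, in an exploratory aim of a 60-patient feasibility study. A careful reader would not treat 0.04 and 0.06 as different findings. All of that stands, and it limits the severity. It is not a reason to keep 1000: the plan itself makes significance the criterion for each path, and the noise is avoidable.

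A reader might go further and infer that the plan's mediation test has a false-positive rate of some 20 to 40%. The documents do not support that, for four reasons:

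- Nowhere do they say that single records will be drawn. The bootstrap is tied to a cited procedure, which may fix the unit but cannot be checked from the documents, and to repeated-measures models with a random intercept. A random intercept does not by itself settle how the data are resampled.
- The inflated rate needs a mediator that truly predicts fatigue. With both legs null, record-level draws gave 2 to 5%.
- The plan first looks for a treatment effect on each mediator. If that step is binding, the rate is 4 to 7% even with record-level draws. The text does not say whether failing it stops the analysis.
- Seven visits do not apply to melatonin or the blood markers, and the plan frames the effect to be explained as the time-by-treatment interaction, where the rates are lower.

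**Conclusion.** The point holds for the number of draws. Under a percentile interval and a two-sided 5% level, 1000 samples give the wrong verdict in about 11% of runs at an exact p of 0.04 and about 20% at 0.06. The error is under 5% at 0.03 or 0.07. With 10,000 samples the errors at 0.04 and 0.06 are about 0.15% or less.

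The resampling unit is something to confirm; the documents do not show it to be an error. If records were drawn, the false-positive rate could reach roughly 20 to 40%, given about seven visits, a treatment main-effect path, a mediator that truly predicts fatigue and no binding earlier test. It was higher still in simulation with equal correlation. It stays near 5% if both legs are null or if the treatment-to-mediator test must be passed first.

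Severity is minor. No primary conclusion rests on these tests, although named mediators could influence the design of the larger study that this trial is meant to inform.

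**What to change.** In the Data Analysis text of section 5(g), replace the bootstrap sentence with wording to this effect: *The significance of each indirect path will be judged from a 95% interval of a named type (for example, percentile), based on 10,000 bootstrap samples with a fixed, recorded seed. Whole patients, with all their visits, will be resampled within arm, and the full mediation model will be refitted in each sample.*

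The cost is a change of wording and some computing time. No new data, visits or patients are needed.

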- Eye Diseases which limit the ability of light to be processed (e.g., untreated cataracts, severe glaucoma, macular degeneration, blindness, pupil dilation problems or retina damage)
- Secondary cancer diagnosis within the last 5 years
- Severe sleep disorders (e.g., Narcolepsy)
- History of bipolar disorder or manic episodes (which is a contra-indication for light treatment)
- Severe psychological impairment (e.g., hospitalization for depressive episode in the past 12 months)
- Previous use of light therapy to alleviate fatigue or depressive symptoms

c) Number of Subjects

 Mount Sinai	Protocol Name:	Systematic Programmed Illumination of Hospital Rooms to Prevent/Reduce Cancer-Related Fatigue during Autologous Stem Cell Transplantation for Multiple Myeloma
	Principal Investigator:	[name]; [contact]
	Primary Contact Name/Contact Info:	[name], [contact], [contact]
	Date Revised:	8/15/2019
	Study Number:	IF# 2517160 HS# 15-00777 GCO#: 15-2009

For this feasibility study, we will recruit 60 participants drawn from the pool of upcoming HSCT admissions to treat MM at the MSH bone marrow transplant (BMT) clinic. Our previous research has demonstrated that at least 40% of this group either suffers from or will develop clinically significant fatigue related to cancer or its treatment.

d) Study Timelines

Total participation in this study is 16-18 weeks, and may vary by hospital admission, length of hospital stay, and expediency of returning study related materials.

Endpoints

The primary endpoints in the proposed study are: 1) Fatigue as measured by a simple Graphic Rating Scale, Multidimensional Fatigue FACIT Fatigue Scale, and The Pittsburgh Sleep Quality Index; 3) Depression as measured by the CES-D; 4) Quality of Life measured by the SF-36 scale; 5) Sleep/wake activity measured using an actigraph; and 7) Biological variables melatonin and inflammatory markers (i.e., IL-1ra, IL-6, MCP-1/CCL2, MIP-1a/CCL3, sTNFr1, sIL-6R, CRP) as obtained via urine and blood analysis.

The secondary endpoints include: 1) the amount of light received by the patient as measured by the Daysimeter; 2) treatment satisfaction using the FACIT-TS-G scale, and 3) Psychological moderators (e.g., emotions, symptom burden) that may affect for whom the treatment is effective.

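### The stated power of 0.96-0.98 (and 0.99) counts all 60 recruits and makes no allowance for the 71% retention the protocol expects, so it is modestly overstated unless nearly all loss comes late or after the visits that carry the effect

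*Combined protocol and SAP*

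**What the plan says.** Section 5(c), Number of Subjects, sets enrolment: "For this feasibility study, we will recruit 60 participants". The Power paragraph in section 5(g) takes results from an earlier light-treatment study in breast cancer, assumes a lag-1 autoregressive structure with autocorrelations of 0.40 to 0.60, and reports: "With alpha equal to 0.05 and a sample size of 30 patients per group, power ranged between 0.96 and 0.98". A second calculation, from a sample of 17 transplant survivors, gives: "In this case, power was 0.99 for autocorrelations ranging between 0.40 and 0.60". The sample size is not restated there.

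Section 2, Preliminary research, says of the investigators' previous studies that "they were able to retain 71% of participants, a retention rate that we also expect for the proposed protocol". It does not say to which visit patients were retained, or when the others left.

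The analysis section says that "hierarchical random effects linear mixed models will be employed for Aims 1 and 2 using MIXED with repeated measures". Section 5(e), Methods, lists six assessments after baseline: three "during the inpatient hospital stay at day of transplant, day + 2, day + 7", then "engraftment day 3 (most likely during week 2-3); (C) one month after hospital discharge; and (D) three months after hospital discharge".

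**The concern.** The power figure and the retention forecast describe the same trial, but only one of them can rest on 60 patients. Thirty per group uses every recruit, while the protocol expects about 29% of them not to be retained. No section inflates the sample, discounts the power or names an expected number of completers.

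Two things depend on this. A reader who takes 0.96-0.98 at face value expects somewhat more power than the trial should deliver on its own retention figure. The Power paragraph also says that the effect-size estimates will guide the size of a larger study. With completers only, their standard error would be 1/sqrt(0.71) = 1.19 times the value at full retention, about 19% larger.

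**Working it through.** **Inputs.** Alpha 0.05, 30 per group, stated power 0.96, 0.98 and 0.99, and autocorrelation 0.40-0.60 come from the Power paragraph in section 5(g). Recruitment of 60 is from section 5(c) and retention of 71% from section 2. Sidedness is not stated, and two-sided is assumed.

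**The plan's own figure.** It cannot be reproduced, because the documents give no effect size, SD, number of measurements or tested contrast. The check takes each stated power as correct at 30 per group, solves for the noncentrality it implies, and rescales that to the expected retention.

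**Expected completers.** 60 x 0.71 = 42.6, about 43 (21.3 per arm). Expected loss is 60 x 0.29 = 17.4, about 17.

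**Completers only, single-degree-of-freedom test (normal).** Noncentrality = z(0.975) + z(power). Rescaled power = Φ(noncentrality x sqrt(0.71) − 1.960), with sqrt(0.71) = 0.8426.

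| Stated power | Noncentrality | x 0.8426 | Power |
|---|---|---|---|
| 0.96 | 1.960 + 1.751 = 3.711 | 3.127 | 0.878 |
| 0.98 | 1.960 + 2.054 = 4.014 | 3.382 | 0.922 |
| 0.99 | 1.960 + 2.326 = 4.286 | 3.612 | 0.951 |

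A one-sided test would give 0.888 / 0.929 / 0.956.

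**Completers only, F tests.** Noncentrality is solved at denominator df 60 − 2 = 58, multiplied by 0.71, and evaluated at 42.6 − 2 = 40.6.

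- Numerator df 1: 0.874 / 0.919 / 0.948
- Numerator df 4: 0.850 / 0.900 / 0.934
- Numerator df 7 (eight visits by treatment, counting the conditional second baseline): about 0.84 / 0.89 / 0.92

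Two-sided completers-only power is therefore about 0.84-0.88 / 0.89-0.92 / 0.92-0.95.

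**Partial records kept.** A mixed model uses the visits a patient did attend, so the drop depends on when patients leave. Assume equal loss in both arms, AR(1) by visit order with correlation ρ, and a constant treatment effect over k visits after baseline. A patient seen at all k visits contributes information proportional to k − (k − 2)ρ. One who misses only the last visit contributes (k − 1) − (k − 3)ρ.

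- *Loss before any on-treatment visit.* If baseline means are taken as equal, these patients add nothing about the effect. The information fraction is 0.71 and power is 0.878 / 0.922 / 0.951, as for completers.
- *Loss only before the last visit.* With k = 6 and ρ = 0.5, the ratio is (5 − 1.5)/(6 − 2) = 0.875 and the information fraction is 0.71 + 0.29 x 0.875 = 0.964. For stated 0.96, power is Φ(3.711 x sqrt(0.964) − 1.960) = 0.954. Over ρ = 0.4-0.6 the three figures become about 0.95 / 0.98 / 0.99, almost no drop.
- *A linear time-by-treatment slope instead of an averaged effect.* With equally spaced visits and loss only before the last visit, power is 0.938-0.947 / 0.966-0.972 / 0.981-0.985. The late visits carry more of a slope, so more is lost.

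**The case against.** The strongest reply has four parts.

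1. **The mixed model keeps partial data.** This is true, and the completers-only figures are the conservative end for that reason. It reduces the loss but does not remove it in general. Recruitment takes place weeks to months before admission, so a patient may leave before any light is given and then contribute little or nothing about the treatment effect.
2. **Retention is undefined and loss may come after discharge.** This stands, and it is why the conclusion is conditional. Hypothesis 1a concerns the hospital stay, where fewer patients may be lost than by three months. Hypothesis 1b, however, concerns one and three months after discharge, where late loss would fall.
3. **The Power paragraph is already cautious, and this is a feasibility study.** It calls power difficult to discuss and offers the figures as interim guidance. Those cautions concern the lack of directly relevant research and the 17-patient source. None concerns attrition. They limit the consequence but do not reconcile the two figures.
4. **A reader can multiply 60 by 0.71.** The completer count is indeed easy to obtain. Its effect on power is not, because the inputs to the calculation are not given.

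The missing sample size for the 0.99 figure is a small gap in detail and is not counted as a fault. Coming straight after the 30-per-group sentence, it is naturally read as the same size.

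**Conclusion.** The omission is clear from the documents: power is stated for every recruit, while 71% retention is expected. Confidence in that is high. Confidence in the sizes is moderate, because they are back-solved from the stated power under assumed contrasts, correlation by visit order and dropout timing. They also ignore any bias from informative dropout.

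Within those limits the overstatement is modest. With completers only, a stated 0.96 loses about 8 to 12 points, 0.98 about 6 to 9, and 0.99 about 4 to 7. With partial records the loss can be close to nil. Power stays above 0.80 in every case computed.

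A reader might infer three stronger things that the documents do not support:

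- **That the figure is miscalculated.** It is stated for 30 per group, and nothing shows it to be wrong at that size.
- **That the trial is underpowered and must enrol about 85 (60/0.71 = 84.5).** That would follow only if 30 completers per group were required. The protocol sets no such requirement, and power stays above 0.80 without it.
- **That about 43 completers breaches the pilot size of at least 55 cited in the Power paragraph.** The text does not say whether that figure counts recruits or completers, and 60 recruits meet it.

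**What to change.** Keep 60 enrolled. Rerun the existing calculation with the same source effects and the same autocorrelation range of 0.40-0.60, adding 71% retention and a stated dropout pattern. Say to which visit the 71% applies. Report power as the resulting range with the completers-only case as its conservative end, and give the expected number of completers (about 43, about 21 per arm) beside it. The back-solved values above show only the likely size and should not be copied in.

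The cost is one rerun and about two sentences in the Power paragraph. The stated power becomes slightly less favourable. Enrolment and procedures do not change.
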